### **5.3.2      *Main Analytical Approach***

The ORR and its 95% CI, calculated by the Clopper-Pearson (exact) method, will be presented by cohort. In conjunction with the ORR, the frequency and proportion in each response category will be reported.

The ORR for subjects treated with GEN3014, as compared to the ORR in subjects treated with daratumumab SC in the Expansion Part B with anti-CD38 mAb-naïve RRMM subjects, will be presented by the response ratio and the corresponding 2-sided 95% confidence interval based on the Miettinen-Nurminen method (Newcombe, 1998). P values will not be presented. Any stratified analysis will be done using the IRT stratification factor used for randomization.

The maximum percentage change from baseline (see further details in Section 5.1.3) at any time on trial, but before the first PD, will be presented using waterfall plots.

Individual subject data listings will be provided to support response derivation.

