### 9.1 Statistical Hypotheses

Objectives and endpoints of the trial are stated in Section 3. There are no pre-defined hypotheses for this trial. The escalation part is designed to determine the RP2D and MTD (if reached), and the Expansion Part A to assess the anti-tumor activity of GEN3014.

In the Expansion Part B (Randomized H2H), the response ratio and the geometric mean ratio of  $C_{\text{trough}}$  on Cycle 3 Day 1 will be derived to describe the proportion of effect of daratumumab SC retained by GEN3014 IV as compared to daratumumab SC. The comparison serves as a preliminary estimation of the relative effect of the 2 anti-CD38 mAb molecules.

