## **9.2.3 Expansion Part B (Randomized H2H): Comparison of GEN3014 IV vs Daratumumab SC in Anti-CD38 mAb-naïve RRMM Subjects**

The comparison of the 2 anti-CD38 mAb molecules will be based on approximately 40 evaluable subjects treated with GEN3014 IV vs 40 evaluable subjects treated with daratumumab SC. The ratio in the response rates between the 2 arms will be described using the Miettinen-Nurminen method ([Newcombe, 1998](#)).

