#### **9.4.3.1 Objective Response Rate and Clinical Benefit Rate**

ORR is defined as the proportion of subjects with a partial response, or better. Summaries of eg, VGPR and CBR will be provided with ORR as appropriate.

Disease-specific best overall response (BOR) will be summarized in conjunction with the ORR. The estimated rates and the exact 2-sided 95% confidence intervals (CI) (using the Clopper-Pearson method) will be summarized. Individual subject data listings will be provided.

The ORR for subjects treated with GEN3014, as compared to the ORR in subjects treated with daratumumab SC in the Expansion Part B with anti-CD38 mAb-naïve RRMM subjects, will be presented by the response ratio and the corresponding 2-sided 95% confidence interval based on the Miettinen-Nurminen method ([Newcombe, 1998](#)). P values will not be presented.

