#### **9.4.6.1 Cycle 3 Day 1 Trough Concentration**

The PAS2 will be used for the analyses presented in this section.

The  $C_{trough}$  on Cycle 3 Day 1 is defined as a secondary endpoint in Expansion Part B, as part of the comparison of the 2 anti-CD38 mAb molecules. The  $C_{trough}$  levels in the 2 arms will be compared by calculating the geometric mean ratio and the corresponding 90% CI.

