### 1.3 Randomization and Blinding

The 1:1 randomization between GEN3014 and daratumumab SC in Expansion Part B will be stratified by body weight at baseline ( $\leq 70$  kg vs  $> 70$  kg), CCI [REDACTED]. The randomization will be administered through a centralized IRT system which will dictate the treatment assignment and matching study drug kit for the subject. The randomization is not blinded.

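### Part B is randomised within body-weight strata, but the main ORR ratio is specified without strata and a stratified version is left optional and undefined

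*SAP*

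**What the plan says.** SAP 1.3 states that the Part B randomisation "will be stratified by body weight at baseline", split at 70 kg. Protocol 4.1, 4.1.4 and 6.4.2.2 say the same. In each place redacted text follows, so whether there is a further factor cannot be known from these documents. SAP 5.3.2 refers to the stratification factor in the singular.

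Protocol 9.2.3 plans "approximately 40 evaluable subjects treated with GEN3014 IV vs 40 evaluable subjects treated with daratumumab SC". Under Protocol 9.4.3.1 the ORR comparison "will be presented by the response ratio and the corresponding 2-sided 95% confidence interval based on the Miettinen-Nurminen method", and SAP 5.3.2 repeats this. Neither mentions strata there, and neither plans P values.

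The only reference to stratified analysis is in SAP 5.3.2: "Any stratified analysis will be done using the IRT stratification factor used for randomization". It names no endpoint, no stratum weights and no rule for small strata. SAP 5.3.3 plans no sensitivity analyses.

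Protocol 6.4.2.2 lets the sponsor replace Part B subjects by treatment arm instead of by stratification factor, if justified. The SAP's version history ties it to the protocol of 18 February 2022 (Amendment 3). Amendment 5 later revised that section to deal with replacement, and the SAP says nothing on it.

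**The concern.** Randomising within strata fixes the stratum mix in each arm, which removes the variation between strata from the comparison. A crude interval still carries that variation in its standard error. If the strata are prognostic, it is wider than necessary and covers more than 95%.

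Two further points do not depend on the size of that gain. First, Part B is purely an estimation exercise, so the ratio and its interval are what it delivers. With the stratified analysis optional and undefined in an open-label trial, the choice of version can be made after responses are known. Second, balance across strata is not assured in the analysed set. Replacement may ignore the strata, and the FAS leaves out randomised subjects who were never dosed (Protocol 9.3). A stratified ratio corrects for imbalance in those factors and a crude ratio does not.

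**Working it through.** **Inputs.** 40 per arm (Protocol 9.2.3). ORR 40% in both arms: Protocol 9.5.1 uses 40% for the GEN3014 lead-in, and Protocol 2.1.1.1 puts daratumumab non-response at about 60%. Two equal strata of 20 per arm, and the stratum-specific ORRs, are assumptions shown as a range. The documents give neither.

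**The plan's own figure.** No power, margin or interval width is stated for Part B, so there is none to reproduce. The related lead-in figure does reproduce: P(≥2 of 10 at 40%) = 1 − 0.6^10 − 10 × 0.4 × 0.6^9 = 0.954, stated as 95%.

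**Method.** The Miettinen-Nurminen limits are the values of R at which

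Z(R) = Σ wᵢ(p₁ᵢ − R·p₀ᵢ) / √(Σ wᵢ²Vᵢ) = ±1.96,

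with wᵢ = n₁ᵢn₀ᵢ/(n₁ᵢ + n₀ᵢ) and Vᵢ = [p̃₁ᵢ(1 − p̃₁ᵢ)/n₁ᵢ + R²p̃₀ᵢ(1 − p̃₀ᵢ)/n₀ᵢ] × Nᵢ/(Nᵢ − 1), where p̃ are the estimates constrained to ratio R. The crude interval is the case of one stratum.

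**Expected-count tables.** Crude, 16/40 vs 16/40: ratio 1.00 (0.582 to 1.718), log-width ln(1.718/0.582) = 1.082. Stratified:

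- 40%/40%: 0.580 to 1.724, log-width × 1.006
- 50%/30%: 0.585 to 1.708, × 0.990
- 60%/20%: 0.602 to 1.660, × 0.937

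**Why the gain grows slowly.** At 40% overall, the binomial variance per subject is 0.4 × 0.6 = 0.24. With two equal, balanced strata, the within-stratum variance is 0.24 − (gap/2)². The true SD of the crude estimate, relative to the SE it is given, is therefore about √[(0.24 − (gap/2)²)/0.24]. At a 40-point gap this is √(0.20/0.24) = 0.913.

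**Simulation.** Runs of 2,000 and 4,000 replicates, true ratio 1. Log-widths agreed to within 0.001 between runs.

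| Stratum ORR | Gap | True SD / crude SE | Log-width, stratified / crude | Crude coverage |
|---|---|---|---|---|
| 40/40% | 0 | 1.000 | 1.001 | 94.7–95.2% |
| 45/35% | 10 | 0.995 | 0.997 | 94.9–95.1% |
| 50/30% | 20 | 0.979 | 0.985 | 94.6–95.3% |
| 55/25% | 30 | 0.952 | 0.962–0.963 | 96.3–96.4% |
| 60/20% | 40 | 0.913 | 0.931–0.932 | 96.9–97.2% |

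The planned method gives less than the SD ratio alone suggests: about 4% instead of 5% at 30 points, and about 7% instead of 9% at 40 points.

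**Four equal strata** (10 per arm each), in case there is a further factor: simulated log-width × 1.004 with no prognostic effect and × 0.983 at 55/45/35/25%. With no effect, the expected-count table gives × 1.020.

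**The case against.** The strongest reply is that nothing turns on this. Protocol 9.1 says "There are no pre-defined hypotheses for this trial", and there are no P values, margin or power. A crude ratio from a randomised comparison is a legitimate descriptive estimate. Any error in its interval is in the conservative direction. No passage says that body weight is prognostic for ORR, and at gaps of 20 points or less the loss is under 2% with nominal coverage. The number of strata is partly redacted, so stratifying could meet sparse cells.

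All of this stands as to size. It does not answer the missing commitment: the SAP allows a stratified analysis without saying whether one will be done, or how. Nor does it answer the possible imbalance after replacement by arm.

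A reader might infer three stronger points that the documents do not support.

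- *That the ORR interval is wider than it should be.* This holds only if the strata are clearly prognostic. With no stratum effect, stratifying widens it slightly.
- *That C_trough needs a weight-adjusted model.* Protocol 9.4.6.1 says the trough "levels in the 2 arms will be compared by calculating the geometric mean ratio and the corresponding 90% CI", with no weight term, although GEN3014 is dosed per kg and daratumumab SC is a flat 1800 mg. Assume log-weight slopes of −1 (flat dose) and +0.25 (per-kg dose), residual log-SD 0.5 and log-weight SD 0.2. An arm-by-weight model evaluated at mean weight then lowers the model SE from 0.116 to 0.112, but the estimator's actual SD stays at 0.116, and coverage of the population ratio falls from 90.3% to 89.1%. The apparent 4% gain is not real for that ratio. A plain stratum term gains under 1% when the weight effects have opposite signs in the two arms (log gaps of +0.4 and −0.2). It would gain more with a sizeable effect in the same direction in both arms, but the documents give no figure for that.
- *That PFS, OS and TTNT need stratified hazard ratios.* The plan describes these by Kaplan-Meier estimates only, and no calculation here supports adding a model.

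**Conclusion.** The point holds as a gap in specification with a modest, conditional effect on precision. Part B is stratified by design, and neither document commits its main ORR ratio to those strata. If the strata do not affect response, the crude interval loses nothing. It is about 1.5% wider than necessary on the log scale at a 20-point gap, about 4% at 30 points and about 7% at 40 points. Crude coverage is near nominal up to 20 points, about 96% at 30 and about 97% at 40. These figures rest on two equal strata, 40 per arm, 40% ORR in both arms and a common ratio of 1.

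Even the largest of these gains only moves 0.58–1.72 to about 0.60–1.66. The case for the change rests as much on analysing by the groups used to randomise, fixing the choice before the data are seen and correcting any stratum imbalance. The crude analysis is not invalid.

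**What to change.** In SAP 5.3.2, make the Miettinen-Nurminen response ratio stratified by the IRT factor(s) the main Part B ORR analysis, with the crude ratio as a supporting result. Pre-specify:

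- the stratum weights, for example n₁n₀/(n₁ + n₀);
- a rule that collapses sparse strata to body weight alone, with its trigger set in advance (for example, fewer than 5 subjects in any arm-by-stratum cell) and, if body weight is the only factor, a statement of when the crude ratio stands in;
- that subjects replaced by arm under Protocol 6.4.2.2 are analysed in their actual stratum.

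Protocol 9.4.3.1 names the Miettinen-Nurminen method without excluding strata, so the method is unchanged; a line in SAP Appendix 1 can record the choice. No change to the C_trough comparison or the time-to-event summaries is asked for here.

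The cost is SAP wording and minor programming before database lock. The downsides are that a collapse rule is needed, and that the interval may be very slightly wider if the strata turn out not to be prognostic: about 0.1% on average with two strata, and up to about 2% with four in the expected-count table.

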## 1 INTRODUCTION

This statistical analysis plan describes in detail the analysis of the endpoints for trial GCT3014-01. GEN3014 (HexaBody®-CD38) is a fully human immunoglobulin (Ig)G1 monoclonal antibody (mAb) targeting the cluster of differentiation (CD)38 antigen. As compared to daratumumab, GEN3014 has a higher affinity for CD38, more potent CDC activity, and stronger inhibition of the CD38 cyclase activity. It is hypothesized that GEN3014 may trigger stronger reversion of the immune suppression in the tumor microenvironment.

GCT3014-01 comprises the following parts (see [Figure 1](#)):

- Phase 1 Dose Escalation Part
  - Dose escalation in RRMM
  - Dose escalation in R/R AML
- Phase 2 Expansion Part A
  - Expansion arm in anti-CD38 mAb-naïve RRMM
  - Expansion arm in anti-CD38 mAb-refractory RRMM
  - Expansion arm in R/R DLBCL
  - Expansion arm in R/R AML
- Phase 2 Expansion Part B
  - A randomized H2H comparison of GEN3014 IV versus daratumumab SC in anti-CD38 mAb-naïve RRMM

The main analysis reporting difference between the parts is the ordering of objectives and the grouping of summary statistics. In the Dose Escalation, the primary objective is to determine the safety profile (summarized by DLTs, AEs and safety laboratory parameters), while in Phase 2 Expansion it is to further characterize the antitumor activity based on disease specific response evaluations:

- The International Myeloma Working Group consensus criteria (IWMG) 2016 for RRMM,
- The revised response criteria 2014 for Hodgkin and non-Hodgkin lymphoma (Lugano classification) for R/R DLBCL, and
- The International Working Group (IWG) 2003 response criteria for R/R AML.

The grouping factor in Dose Escalation is the dose level per disease type while in Phase 2 Expansion the results will be summarized by the (disease) cohort. Besides this and the different disease specific response criteria, the underlying details of the analyses and the statistical methodologies do not differ between escalation and expansion, or between diseases. This SAP is thus used for both parts, with above differences noted. To ease the presentation of the planned analysis, the word “cohort” will be used throughout, but this can also be thought of as the dose level in Dose Escalation. Layouts, programming notes and titles for the tables, listings and figures are further specified in the Data Presentation Specification (DPS).

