**Table 5: Analysis visit windows for efficacy summary listings in R/R DLBCL**

Analysis period	Target day (visit window per protocol)	Analysis visit window	Label on output
Baseline	1 (pre-dose C1D1)	Last data point prior to dosing	Baseline
Scheduled on-treatment disease assessments Week 6,	42 ( $\pm 3$ )	1 to 63	Week 6
	84 ( $\pm 3$ )	64 to 105	Week 12

12, 18, and 24, then every 24 weeks thereafter	126 ( $\pm$ 3)	106 to 147	Week 18
	168 ( $\pm$ 3)	148 to 252	Week 24
	336 ( $\pm$ 3)	253 to 420	Week 48
	...	...	...
Unscheduled	-	-	Unscheduled <Day x>
End of treatment	-	-	End of treatment

Response assessments should be performed until confirmation of disease progression, start of new anti-cancer therapy, withdrawal of consent, or death, whichever comes first.

Details on how to slot subject data that systematically is performed off schedule is provided in the ADaM specification, but no data should be disregarded for efficacy evaluations due to this windowing.

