### 5.1.3 *Disease Specific Response Considerations*

Each individual timepoint response per disease specific criteria is reported by investigator in eCRF. The best overall response (BOR) will be derived for the purpose of analyzing efficacy endpoints (ORR, DOR and CBR). Timepoint responses recorded after new anticancer therapy or progressive disease (PD), will be excluded from BOR derivation. Section 5.1.3.1 to 0 details disease specific derivations.

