##### **Key response variables**

Response to GEN3014 or daratumumab SC in RRMM subjects will be assessed in accordance with the IMWG Response Criteria (Kumar et al., 2016). Centrally analyzed samples will be used by the investigator to report the response in eCRF. The best overall response in RRMM subjects can be one of sCR, CR, VGPR, PR, MR, SD, PD or NE.

To support the responses based on the IMWG criteria, a detailed efficacy listing with below parameters is planned:

- SPEP as measured by the total amount of abnormal protein in the serum electrophoresis. (This may constitute one or more abnormal spikes in different protein bands.)
  - With IFE interpretation of the serum
- UPEP as measured by the total amount of abnormal protein in the urine electrophoresis
  - With IFE interpretation of the urine
- FLC with the kappa to lambda ratio, and the difference between the two chains
- The sum of the product of the perpendicular diameters (SPD) of the plasmacytomas (or longest diameter if only 1 is reported)
  - Radiated plasmacytomas are not evaluable for response, and can only be used to monitor progression
- Bone marrow plasma cells, as assessed by aspiration and/or biopsy.
  - If both aspiration and biopsy is obtained at same time point the highest value will be used
- Lytic bone lesions are used only to assess progression
  - In particular, the bone lesion eCRF assessment form will be used to assess progression with the two questions *Is there definite increase in the size of existing bone lesions since baseline?* and *Is there development of new bone lesions since baseline?*
  - For descriptive purposes only, the number of bone lesions will be reported as follows: The number of lytic lesions is assessed on the skeletal eCRF assessment form, and reported as 0, 1, 2, 3, >3, or “Unable to Determine” per anatomic location. The following rules are applied when deriving the total number of bone lesions:
    - If no anatomic location has “>3” or “Unable to Determine”: sum the numerical values and sort into one of the following categories: “0”, “1-3”, or “4-10” or “>10”
    - If one or more anatomic location(s) has “>3” or “Unable to Determine”: the total number of lytic bone lesions is set to “Unable to Determine”

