#### ***5.3.1 Definition of Endpoint(s)***

ORR is defined as the proportion of subjects in the analysis population (FAS is used for primary analysis) with a BOR of partial response (PR) or better according to the disease specific criteria. In detail, the disease-specific definitions of ORR are

- RRMM: a BOR of PR, VGPR, CR or sCR
- R/R DLBCL: a BOR of PR or CR
- R/R AML: a BOR of MLFS, PR, CRp, CRi, or CR.

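### The waterfall plots stop before the first PD, so read literally they omit subjects who progress at their first assessment (SAP 5.3.2); ORR is unaffected

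*SAP*

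**What the plan says.** SAP 5.3.2 describes the plotted quantity as "The maximum percentage change from baseline (see further details in Section 5.1.3") and says that the value "at any time on trial, but before the first PD, will be presented using waterfall plots". Section 5.1.3 lists the myeloma parameters that go into a supporting listing and gives the lymphoma response tables. It does not define the plotted change, its direction or its time window.

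The response derivation uses a different window. Under SAP 5.1.3, "Timepoint responses recorded after new anticancer therapy or progressive disease (PD), will be excluded from BOR derivation". The PD time point itself therefore counts. For myeloma, SAP 5.1.3.1 states: "The best overall response in RRMM subjects can be one of sCR, CR, VGPR, PR, MR, SD, PD or NE".

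For ORR, SAP 5.3.1 says that the "FAS is used for primary analysis". In the same paragraph as the ORR, SAP 5.3.2 adds that "the frequency and proportion in each response category will be reported". SAP section 1 leaves figure detail to another document: "Layouts, programming notes and titles for the tables, listings and figures are further specified in the Data Presentation Specification (DPS"). That document was not available for this review.

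**The concern.** A waterfall plot is read as a picture of the whole cohort, and its right-hand side should show the subjects who did worst. If only values before the first PD are eligible, a subject with PD at the first assessment has none, and the SAP gives no substitute: no value from the PD visit, no placeholder and no count of subjects not shown. The losses are selective, because they fall on non-responders with the earliest failures.

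Early PD is plausible here. The population is relapsed or refractory, myeloma response assessment starts at Cycle 2 Day 1 (Protocol Table 1-12), and the first scheduled lymphoma assessment is at Week 6 (SAP Table 5).

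The figure is only descriptive, but so is the whole comparison in this trial: there are no hypotheses and no P values, and the Protocol synopsis says the sponsor will use the Part B data to guide further development. In Part B an arm with more early progressors would lose more bars and so look better in the figure.

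**Working it through.** The plan states no figure for the waterfall plots, so there is nothing to reproduce. The check compares the two windows and then sizes the effect under stated assumptions.

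**1. Windows side by side, for a subject whose first post-baseline assessment is PD**

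- Best overall response (SAP 5.1.3): the PD time point is used, and the subject's best response is PD.
- ORR (SAP 5.3.1): the subject is in the denominator as a non-responder.
- Response-category table (SAP 5.3.2): the subject is counted under PD.
- Waterfall plot (SAP 5.3.2): no eligible value, so no bar.

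There is a second mismatch. The response rule also drops time points after new anti-cancer therapy; the plot rule does not.

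**2. Inputs for the illustration**

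- N = 40: the maximum DLBCL cohort size (SAP 5.7.2), and also the planned size of each Part B arm (SAP section 3).
- ORR of 20% and 40%: the undesirable and desirable rates in SAP 5.7.2; 40% is also the rate used in SAP 5.7.1 for the myeloma lead-in. Responders R = 8 or 16.
- m = number with PD at first assessment: not given in the documents. Assumed 5%, 10%, 20%, 30% and 40% of 40, so m = 2, 4, 8, 12 and 16.
- Every other subject is assumed to have a post-baseline value.

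**3. Formula**

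Responder share of bars = R / (N − m), compared with ORR = R / N.

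| m | Bars | R = 8 (ORR 20.0%) | Excess, points | R = 16 (ORR 40.0%) | Excess, points |
|---|---|---|---|---|---|
| 2 | 38 | 21.1% | 1.1 | 42.1% | 2.1 |
| 4 | 36 | 22.2% | 2.2 | 44.4% | 4.4 |
| 8 | 32 | 25.0% | 5.0 | 50.0% | 10.0 |
| 12 | 28 | 28.6% | 8.6 | 57.1% | 17.1 |
| 16 | 24 | 33.3% | 13.3 | 66.7% | 26.7 |

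**4. Unequal arms in Part B**

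Take 16 responders of 40 in each arm, so the ORR is 40% in both and the response ratio is 1. If 4 subjects in one arm and 12 in the other have PD at first assessment, the responder shares of bars are 16/36 = 44.4% and 16/28 = 57.1%. The arm with three times as many early progressors looks better by 12.7 points. The 4 and 12 are assumptions.

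**5. After the change**

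If the PD value is eligible, m no longer reduces the bars. The shares return to 8/40 = 20.0% and 16/40 = 40.0%, provided all subjects have a post-baseline value.

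**The case against.** The strongest reply is that no estimate depends on this figure. It shows percentage change, not ORR. The ORR, its Clopper-Pearson interval and the response ratio do not use it, the interim rules count responders, and early progressors are visible in the response-category table and the listings. All of that stands. A reader might infer from the placement under the primary analysis that the primary result is biased; the documents do not support that.

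A second reply concerns direction. One might infer that a PD value can never be the largest reduction, so that the rule does nothing except delete early progressors. That is wrong on two counts. PD can be declared on a new lesion (Protocol Appendix 9; SAP Table 7) or on bone lesions (SAP 5.1.3.1) while the plotted marker is still falling, so an omitted bar need not be an increase. The rule also removes values after the first PD, and such values can exist: for lymphoma, "Response assessments should be performed until confirmation of disease progression", and in Part B myeloma biochemical PD needs two consecutive assessments (Protocol Table 1-12 footnotes).

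A third reply is that the missing bar is itself an inference. The SAP does not say whether the first PD is the initial or the confirming assessment; on the second reading, a subject with biochemical PD would have one usable value. The data presentation specification might also add a footnote. This limits the certainty. But the specification is cited for layouts, programming notes and titles, and if it follows the SAP's selection rule it cannot plot the PD value.

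Finally, subjects with no post-baseline value lack a bar under any wording. That is true, and it is why the fix includes a footnote.

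**Conclusion.** The point holds as a low-severity inconsistency in a descriptive figure. Read literally, the plot window is narrower than the SAP's own response window and leaves out subjects whose first post-baseline assessment is PD. The likely result is a figure more favourable than the ORR beside it, possibly unequally between the Part B arms. Overstatement is the expected direction, not a certainty.

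The excess of about 1 to 13 points (ORR 20%) or 2 to 27 points (ORR 40%) rests on three assumptions: that 5% to 40% of 40 subjects have PD at first assessment, that the literal reading is applied, and that all other subjects have a value. Responders as a share of bars is a way to size the visual effect; the SAP does not report that statistic. It would be going too far to say that the trial's activity estimate is overstated: the reported rate is the ORR on the full analysis set, and that is unchanged.

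**What to change.** In SAP 5.3.2, replace the restriction to values before the first PD with: *up to and including the first PD, and before new anti-cancer therapy*. This matches the response window in SAP 5.1.3. Add a footnote to each plot giving the number of full-analysis-set subjects without a bar and the reason, by arm in Part B.

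In the same edit, state for each disease which parameter is plotted, that the bar is the largest reduction (or the smallest increase where there is no reduction), and whether the first PD means the initial or the confirming assessment. The direction matters once PD values are eligible: otherwise the maximum change could be read as the largest increase, and bars would change for subjects who progressed later.

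The cost is one phrase, a footnote and a short definition. It needs no new data and has no effect on sample size or on any reported estimate.
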